7.11.1.3.2 Clinical Global Impression Improvement: Investigator –Rated (CGI-I)

The Clinical Global Impression – Improvement (CGI-I) assessment is a 7-point scale that requires the clinician to assess how much the participant's illness has improved or worsened relative to a baseline state at the beginning of the intervention, and rated as: 1, very much improved; 2, much improved; 3, minimally improved; 4, no change; 5, minimally worse; 6, much worse; or 7, very much worse.³⁹

Completion of this scale requires the clinician to rate how much the participant's illness (including behavioral and adaptive functioning) has improved or worsened relative to a baseline state. The CGI-I must be administered by the same rater for a given participant at all applicable visits throughout the trial.

7.11.1.4 VAS Rating Scale

In an attempt to measure the level of behavioral difficulty experienced by the parent/caregiver with respect to the child with FXS, the VAS will allow parents to mark on a visual line measuring 10 cm with one side marked "worst behavior" and the other side marked "best behavior." The caregiver will rate the participant's behavior with respect to three domains: daily functioning, anxiety/irritability and language; with guidance form the investigator, the caregiver will select a behavior that is a problem affecting function within each domain that will be assessed throughout the study. The horizontal marks are measured in centimeter distance where they call from the "good behavior" side so that improvements or worsening of behavior over the treatment period can be evaluated. The VAS has been successfully used in multiple clinical trials conducted in the FXS population.⁴⁰ The caregiver completing the assessment should remain the same at all applicable visits throughout the trial.

7.11.1.5 Aberrant Behavior Checklist (ABC)

The Aberrant Behavior Checklist- Community Edition (ABC) is a 58-item parent/caregiver rating scale used to assess behaviors across five dimensions or subscales: irritability, hyperactivity, lethargy/withdrawal, stereotypy, and inappropriate speech.⁴¹ Items are evaluated on a four-point Likert scale ranging from 0 (not at all a problem) to 3 (the problem is severe in degree). This scale has been used extensively in FXS in clinical trials and other projects. The ABC will be scored using the FXS-specific factoring system (ABC-FX). The caregiver completing the assessment should remain the same at all applicable visits throughout the trial.

7.11.1.6 Anxiety Depression and Mood Scale (ADAMS)

The ADAMS (Anxiety, Depression, and Mood Scale) is a 28-item behavior-based informant instrument rated by the parent/caregiver and designed to assess anxiety, depression and mood disorders in individuals with intellectual disability.⁴² Items are rated on a scale of 0 ("behavior has not occurred, or is not a problem") to 3 ("behavior occurs a lot, or is a severe problem"). The scale is composed of 5 factors which address: Manic/Hyperactive Behavior. Depressed Mood, Social Avoidance, General Anxiety and Obsessive/Compulsive Behavior. A caregiver identified upon enrollment of participant should have intimate knowledge of the participant's situation and level of impairment to be able to provide accurate information as required to complete the ADAMS. The caregiver completing the assessment should remain the same at all applicable visits throughout the trial.

7.11.1.7 Vineland-3 Rating Scale

The Vineland Adaptive Behavior Scales, Third Edition (Vineland-3)⁴³ assesses adaptive behavior in five domains, each with subdomains:

- 1. Communication
 - Subdomains: Receptive, Expressive, Written
- 2. Daily Living Skills

o Subdomains: Personal, Domestic, Community

- 3. Socialization
 - o Subdomains: Interpersonal Relationships, Play and Leisure, Coping Skills
- 4. Motor Skills
 - Subdomains: Fine Motor, Gross Motor
- 5. Maladaptive Behavior
 - Internalizing, Externalizing, Critical Items

The Vineland-3 will be administered as a standardized interview to a parent/caregiver by trained study staff trained and authorized to perform the interview. The Vineland-3 must be administered by the same rater for a given participant at all applicable visits throughout the trial. The caregiver completing the assessment with the study staff member should also remain the same at all applicable visits throughout the trial.

7.11.1.8 Event-Related Potentials (ERP)

Event-Related Potentials (ERPs) enable extraction of neural responses associated with specific sensory, cognitive, or motor events from an overall EEG.^{44,45} Auditory stimuli are presented and EEG events assessed in relation to timing of the stimuli. For this study, an ERP protocol developed to measure resting state delta and alpha power, alpha responses to eye closure, CHIRP responses,⁴⁶ and processing of oddball stimuli relative to standards⁴⁷ will be used. This protocol has shown feasibility in prior studies. The EEGs will be read by [name] who has developed multiple ERP protocols and has extensive experience in ERP evaluation.

7.11.1.9 Eye Tracking

Eye tracking has been successfully used to assess social gaze in FXS.⁴⁸ Testing will be conducted in a quiet room with the lights turned off. The eye tracker (Tobii) will be calibrated for each participant at the beginning of each session. Following calibration, participants will view pictures shown on the screen. Each assessment begins with presentation of a scrambled face image for 1 s followed immediately by its matched face image for 3 s. An inter-trial interval (ITI) containing a uniform grey

Page 26 of 42

screen is shown for 0.5, 1, or 2 s, randomly determined. The order of face presentation is pseudorandomized and each eye tracking session lasts approximately 6 min. Measurements include looking time to the eye region of interest (ROI), and number of fixations to the eye ROI, as well as pupil dilatation by pupilometry. These measurements have been shown to have good test-retest reproducibility. All measurements are analyzed offline by a trained specialist.

7.11.2 Timing of Efficacy Assessments

7.11.2.1 Baseline (Period 1/Day 1)

The following exploratory efficacy assessments will be performed at Baseline (Period 1/ Day 1, prior to randomization):

- NIH Toolbox Cognitive Battery for Intellectual Disabilities (NIH-TCB)
- Test of Attentional Performance (KiTAP)
- Clinical Global Impression Severity Investigator rated (CGI-S)
- VAS Rating Scale using participant-specific behavioral anchors
- Aberrant Behavior Checklist (ABC)
- Anxiety, Depression, and Mood Scale (ADAMS)
- Vineland-3 Rating Scale
- Event-Related Potentials (ERP)
- Eye Tracking

7.11.2.2 Week 4, 8, 12, 16 (end Periods 1 through 4)

The full battery of cognitive, behavioral and pharmacodynamic tests will be performed at Week 4 of each Period:

- NIH Toolbox Cognitive Battery for Intellectual Disabilities (NIH-TCB)
- Test of Attentional Performance (KiTAP)
- Clinical Global Impression Severity Investigator rated (CGI-S)
- Clinical Global Impression Improvement Investigator rated (CGI-I)
- Visual Analog Scale (VAS) assessment of participant-specific behavioral anchors
- Aberrant Behavior Checklist (ABC)
- Anxiety, Depression, and Mood Scale (ADAMS)
- Event-Related Potentials (ERP)
- Eye Tracking
- Vineland-3 Rating Scale

8 EVALUATION AND REPORTING OF ADVERSE EVENTS

8.1 Adverse Events

An adverse event is defined as any untoward medical occurrence in a clinical investigation participant administered a pharmaceutical product, which does not necessarily have a causal relationship with this treatment. An adverse event can therefore be any unfavorable and/or unintended sign (including an abnormal laboratory finding), symptom, or disease temporally associated with the use of an investigational medicinal product, whether or not related to the investigational medicinal product. All adverse events, including observed or volunteered problems, complaints, or symptoms, are to be recorded on the appropriate CRF.

Adverse events, which include abnormal and clinically significant clinical laboratory test variables, will be monitored and documented from the time Informed Consent until study participation is

complete (the Follow-up Visit). Participants should be instructed to report any adverse event that they experience to the Investigator. Beginning with the signing of the informed consent until the time of the first dose of study drug, investigators should make updates to medical history and record any pre-existing medical condition or signs or symptoms that changes in severity, frequency, or seriousness in the medical history. Serious adverse events that occur prior to the first dose of study drug should be reported as an update to medical history as well as be reported on the appropriate adverse event CRF.

Beginning with the first dose of study drug, investigators should make an assessment for adverse events at each visit and record all adverse events, non-serious and serious, on the appropriate adverse event CRF.

Wherever possible, a specific disease or syndrome rather than individual associated signs and symptoms should be identified by the Investigator and recorded on the CRF. However, if an observed or reported sign or symptom is not considered a component of a specific disease or syndrome by the Investigator, it should be recorded as a separate adverse event on the CRF. Additionally, the condition that led to a medical or surgical procedure (e.g., surgery, endoscopy, tooth extraction, or transfusion) should be recorded as an adverse event, not the procedure. Concomitant procedures should be recorded as such on the appropriate CRF.

Any medical condition already present prior to the participant taking the first dose of study drug should be reported in the medical history. Any SAEs occurring prior to the first dose of study drug should be reported as an update to medical history as well as an adverse event. Any pre-existing medical condition or signs or symptoms that changes in severity, frequency, or seriousness after the participant takes the first dose of study drug and through the Follow-up Visit should be reported as an adverse event.

Clinically significant abnormal laboratory values or other examinations (e.g., ECG) that are detected after the first dose of study drug and worsen during the study should be reported as adverse events. An abnormal laboratory result that is not verified by repeat testing does not necessitate reporting as an adverse event. The Investigator will exercise his or her medical, scientific, and clinical judgment in deciding whether an abnormal laboratory finding or other abnormal assessment is clinically significant. Clinically significant abnormal laboratory values occurring during the clinical study will be followed until repeat tests return to normal, stabilize, or are no longer clinically significant. Any abnormal test that is determined to be an error does not require reporting as an adverse event. Treatment of any adverse reactions will be evaluated and managed by a physician.

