7.9 Management of Abnormal Clinical Laboratory Tests

It is the Investigator's responsibility to review the results of all lab tests as they become available and to document their review by signing and dating the lab report. For each lab test outside of the laboratory normal range, the Investigator must ascertain if this is a clinically significant change from baseline for the individual participant. This determination does not necessarily need to be made the first time an abnormal lab is observed. The Investigator may repeat the lab test or request additional tests to verify the results of the original lab test.

All clinically significant laboratory abnormalities occurring during the study that were not present at baseline should be followed and evaluated with additional tests if necessary, until determination of the underlying cause or adverse event resolution.

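### Section 8.1's laboratory adverse-event rule asks for worsening as well as new onset, which conflicts with the scope statement in 8.1 and with 7.9 and 10.5

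*Combined protocol and SAP*

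**What the plan says.** Section 8.1 gives one specific rule for laboratory findings. It applies to clinically significant values, and those "that are detected after the first dose of study drug and worsen during the study should be reported as adverse events". The next sentence reads: "An abnormal laboratory result that is not verified by repeat testing does not necessitate reporting as an adverse event". Section 7.9 leaves repeats to the investigator's choice: "The Investigator may repeat the lab test or request additional tests to verify the results of the original lab test".

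Other text is broader:

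- The definition at the start of 8.1: "An adverse event can therefore be any unfavorable and/or unintended sign (including an abnormal laboratory finding), symptom, or disease".
- The scope statement in 8.1: "Adverse events, which include abnormal and clinically significant clinical laboratory test variables, will be monitored and documented".
- Section 7.9: "All clinically significant laboratory abnormalities occurring during the study that were not present at baseline should be followed and evaluated".
- Section 10.5 counts clinically meaningful laboratory abnormalities among the adverse events to be analysed.

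The synopsis (Safety Analyses) has adverse events tabulated separately for placebo, EM, EM + 5-HTP and 5-HTP. Section 3.4.3 lists clinical laboratory evaluations as a safety endpoint alongside treatment-emergent adverse events.

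**The concern.** The specific rule joins two conditions with *and*: the abnormality is detected after dosing starts, and it worsens. A usual treatment-emergent criterion would join them with *or*: new on treatment, or present before and worse since. As written, a participant with a clinically significant abnormality that appears at Week 4 and is unchanged at Week 8 does not meet the sentence.

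A person completing the case report form has two criteria and no statement of which governs. The specific sentence is the one likely to be applied, and it is the narrower. The adverse-event table is where a laboratory finding carries its severity and relatedness. With 15 participants and one column per treatment, one or two findings handled differently would visibly change a column.

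**Working it through.** The plan gives no figure to reproduce. The check compares the rules and then counts draws.

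**Step 1: the rules side by side.** All rows concern clinically significant findings. Clinically meaningful in 10.5 is assumed to mean the same thing.

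| Finding | Specific rule, 8.1 | Scope statement, 8.1 | 7.9 | 10.5 |
|---|---|---|---|---|
| New, then worse | Report | Adverse event | Follow | Counted |
| New, then stable | Not called for | Adverse event | Follow | Counted |
| New, never repeated | Not called for; worsening not shown | Adverse event | Follow | Counted |
| Present before dosing, then worse | Not called for by this sentence | Adverse event | Outside its wording | Counted |

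The second and third rows are the contradiction. The fourth is weaker, because the preceding paragraph of 8.1 makes a pre-existing condition, sign or symptom that changes in severity after first dose an adverse event. That arguably covers a laboratory value.

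**Step 2: the repeat-test sentence.** It can mean that a repeat was done and did not confirm the result, or that no repeat was done. Results found to be errors have their own sentence in 8.1, so this one reaches further than errors. It is not limited to results judged clinically insignificant. On the second meaning, together with the optional repeat in 7.9, it removes the duty to report a clinically significant result that nobody repeated. Against that, 8.1 also has clinically significant values followed with repeat tests until they normalise, stabilise or lose significance. The section therefore points both ways.

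**Step 3: what scheduled draws can show.** Inputs: 15 participants (Section 6.1); post-dose chemistry, hematology and urinalysis at Weeks 4, 8, 12 and 16 (Sections 9.3.3 and 14.1); a telephone call only at Week 17 (Section 9.3.4); no washout (Section 4.1); fixed order EM, EM + 5-HTP, 5-HTP, placebo.

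- Planned post-dose draws if all complete: 15 × 4 = 60.
- Draws followed by another scheduled draw under the same treatment: 0 of 60, since each period has one.
- Draws whose next scheduled draw falls under the next treatment (Weeks 4, 8, 12): 15 × 3 = 45, and 45/60 = 75%.
- Draws with no later scheduled draw (Week 16, all on placebo): 15/60 = 25%.

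An abnormality arising on EM and found at Week 4 can therefore first meet the worsening condition at Week 8, on EM + 5-HTP. Neither 10.5 nor the synopsis says whether such an event belongs to the period of onset or of worsening.

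**The case against.** The strongest reply is that the narrow sentence controls nothing. It says what should be reported and does not say that other findings may not be. The same section defines adverse events broadly and, from first dose, has investigators record all of them. The repeat-test sentence removes an obligation and forbids nothing. Clinically significant values are to be followed with repeat tests, so an unscheduled test could show worsening after Week 16. Laboratory values are also a separate endpoint, summarised whatever their adverse-event status.

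Much of this stands, and it rules out several readings that a reader might infer:

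- That a laboratory finding is an adverse event only when it worsens. The text is not exclusive.
- That every unrepeated result is exempt. The wording is permissive and ambiguous, and other text expects repeats of significant values.
- That a Week 16 finding can never be shown to worsen. This is true only of scheduled draws.
- That such findings vanish from the safety endpoints. Observed values and changes from baseline are still summarised for continuous parameters.

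What does not stand is that the broad text settles the matter. It contradicts the narrow sentence, and nothing gives it precedence. Follow-up testing does not repair the gap either: it may stop once a value stabilises, and a new, stable abnormality is exactly what the sentence leaves out. The laboratory summaries help only in part. Section 10.5 plans summary statistics for continuous parameters and names no shift table or out-of-range count. A categorical urinalysis finding would not appear in them, and a minimum or maximum does not show clinical significance or relatedness.

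**Conclusion.** The point holds as an internal contradiction in the laboratory adverse-event criterion, with an ambiguous repeat-test sentence beside it. If sites apply the specific sentence literally, the treatment-emergent adverse-event table can omit new, stable, clinically significant abnormalities, and can place others under the treatment that followed the one on which they arose.

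The number of events affected cannot be estimated, because the documents give no rate of laboratory abnormalities. The 25% is only the share of planned draws with no later scheduled draw, assuming all 15 participants complete. A reader might take it as the share of adverse events lost; nothing in the documents supports that.

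The net direction of any bias is also open. The last-draw problem falls on the placebo column, while unreported stable findings could come from any of the three active periods. The consequence is confined to the adverse-event tables of an exploratory, descriptive study, but safety is a stated objective and the correction is cheap.

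**What to change.** Make two changes in Section 8.1.

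1. Replace the condition in the laboratory sentence so that it covers clinically significant abnormalities *that are new after the first dose of study drug, or were present before it and worsen*. A new finding then becomes reportable when it is detected, without waiting for a draw under the next treatment. The sentence also agrees with the scope statement in 8.1 and with 7.9 and 10.5.
2. Limit the repeat-test exemption to results that a repeat test failed to confirm, or that were shown to be in error. A clinically significant result that was not repeated then stays reportable.

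The cost is two reworded sentences and perhaps a few more laboratory adverse events recorded. No tests or visits are added.

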8.2 Definitions

8.2.1 Adverse Drug Reaction

For adverse events with a causal relationship to study drug, follow-up by the Investigator will be required until the event or its sequelae resolve or stabilize to a level acceptable to the Investigator.

8.2.2 Unexpected Adverse Event/ Unexpected Adverse Drug Reaction

An unexpected AE/unexpected suspected adverse reaction is an AE or suspected adverse reaction that is not listed in the Investigator Brochure or is not listed at the specificity or severity that has been observed; or, if an Investigator Brochure is not required or available, is not consistent with the

risk information described in the general investigational plan or elsewhere in the current application, as amended.

8.2.3 Serious Adverse Events

An adverse event or adverse reaction is considered serious if, in the view of either the Investigator or Sponsor, it results in any of the following outcomes:

- Death;
- A life-threatening adverse event;
- NOTE: An adverse event or adverse reaction is considered "life-threatening" if, in view of either the Investigator or Sponsor, its occurrence places the participant at immediate risk of death. It does not include an event that, had it occurred in a more severe form, might have caused death.
- Requires hospitalization or prolongation of existing hospitalizations;
- NOTE: Any hospital admission with at least one overnight stay will be considered an inparticipant hospitalization. An emergency room visit without hospital admission will not be recorded as a SAE under this criterion, nor will hospitalization for a procedure scheduled or planned before signing of informed consent. However, unexpected complications and/or prolongation of hospitalization that occur during elective surgery should be recorded as adverse events and assessed for seriousness. Admission to the hospital for social or situational reasons (i.e., no place to stay, live too far away to come for hospital visits) will not be considered inparticipant hospitalizations.
- A persistent or significant disability/incapacity or substantial disruption of the ability to conduct normal life functions;
- A congenital anomaly/birth defect; or
- An important medical event.

NOTE: Important medical events that may not result in death, be life-threatening, or require hospitalization may be considered an SAE when, based upon appropriate medical judgment, they may jeopardize the participant and may require medical or surgical intervention to prevent one of the outcomes listed in this definition. Examples of such medical events include allergic bronchospasm requiring intensive treatment in an emergency room or at home, blood dyscrasias or convulsions that do not result in in participant hospitalizations, or the development of drug dependency or drug abuse.

8.3 Assessment of Adverse Events by the Investigator

8.3.1 Causality/Relatedness

The relationship of an adverse event to the administration of the study drug is to be assessed by the Investigator according to the following definitions:

Not Related (unlikely related, unrelated, not related, no relation) – The time course between the administration of study drug and the occurrence or worsening of the adverse event rules out a causal relationship and/or another cause (e.g., medical history, concomitant drugs, therapies, and complications) is suspected.

Related (possibly related, related) – The time course between the administration of study drug and the occurrence or worsening of the adverse event is consistent with a causal relationship and no other cause (e.g., medical history, concomitant drugs, therapies, and complications) can be identified.

The definition implies a reasonable possibility of a causal relationship between the event and the study drug. This means that there are facts (evidence) or arguments to suggest a causal relationship.

The following factors should also be considered:

- The temporal sequence from study drug administration The event should occur after the study drug is given. The length of time from study drug exposure to event should be evaluated in the clinical context of the event.
- Underlying, concomitant diseases (medical history) Each report should be evaluated in the context of the natural history and course of the disease being treated and any other disease the participant may have.
- Concomitant drug The other drugs the participant is taking or the treatment the participant receives should be examined to determine whether any of them might be recognized to cause the event in question.
- Known response pattern for this class of study drug Clinical and/or preclinical data may indicate whether a particular response is likely to be a class effect.
- Exposure to physical and/or mental stresses The exposure to stress might induce adverse changes in the recipient and provide a logical and better explanation for the event.
- The pharmacology and PK of the study drug The known pharmacologic properties (absorption, distribution, metabolism, and excretion) of the study drug should be considered.

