5.2 Participant Inclusion Criteria

- 1. Participant is male aged 18 to 45 years, inclusive.
- 2. Participant has Fragile X Syndrome with a molecular genetic confirmation of the full Fragile X Mental Retardation 1 (FMR1) mutation (≥200 CGG repeats).
- 3. Current treatment with no more than 3 prescribed psychotropic medications. Anti-epileptic medications are permitted and are not counted as psychotropic medications if they are used for treatment of seizures. Anti-epileptics for other indications, such as the treatment of mood disorders, count towards the limit of permitted medications.
- 4. Permitted concomitant psychotropic medications must be at a stable dose and dosing regimen for at least 2 weeks prior to Screening and must remain stable during the period between Screening and the commencement of study medication.
- 5. Anti-epileptic medications must be at a stable dose and dosing regimen for 12 weeks prior to Screening and must remain stable during the period between Screening and the commencement of study medication.
- 6. Participants with a history of seizure disorder who are currently receiving treatment with anti-epileptics must have been seizure-free for 3 months preceding screening or must be seizure-free for 3 years if not currently receiving anti-epileptics.
- 7. Behavioral and therapy treatments/interventions must be stable for 4 weeks prior to Screening and must remain stable during the period between Screening and the commencement of study medication, and throughout the study. Minor changes in hours or times of therapy that are not considered clinically significant will not be exclusionary.

Changes in therapies provided through a school program, due to school vacations, are allowed.

- 8. Participant must be willing to practice barrier methods of contraception while on study, if sexually active. Abstinence is also considered a reasonable form of birth control in this study population.
- 9. Participant has a parent, legal authorized guardian or consistent caregiver.
- 10. Participant and caregiver are able to attend the clinic regularly and reliably.
- 11. Participant is able to swallow tablets and capsules.
- 12. For participants who are not their own legal guardian, participant's parent/legal authorized guardian is able to understand and sign an informed consent form to participate in the study.
- 13. If participant is his/her own legal guardian, he/she can understand and sign informed consent to participate in the study.

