10.5 Safety Analysis

Safety analysis will be based on all participants receiving at least one dose of study medication. Treatment emergent AEs will be summarized based on the frequency of AEs and their severity for all dosed participants. Adverse Events (AEs), including clinically meaningful laboratory abnormalities and significant behavioral changes, will collected. AE severity and relatedness to treatment will be assessed. AEs will be tabulated for placebo and BPN14770 treatments using preferred terms and system organ classes. Summaries will also be provided by severity and relationship to treatment. Serious Adverse Events (SAEs) will be summarized separately, in a manner similar to that used for Adverse Events.

Overall safety and tolerability will be assessed by clinical and/or statistical review of all safety parameters including adverse experiences, laboratory values, vital signs, physical exams, and ECG data. General clinical and laboratory adverse events will be presented in frequency tables. Summary statistics (n, mean, SD, median, and range (minimum, maximum) will be tabulated for the observed values and the change (or percent change) from baseline for all continuous parameters for vital signs and laboratory tests.

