12.2 Institutional Review Board (IRB)

Before initiation of the study, the Investigator will obtain approval or favorable opinion of the research protocol, informed consent form, and any advertisement for participant recruitment from an IRB complying with the provisions specified in 21 CFR §56 and applicable pertinent state and federal requirements of each participating location including International Conference on Harmonization (ICH) and GCP guidelines.

Institutional review boards must be constituted according to the applicable laws. It is the responsibility of each investigational site to submit the protocol, Investigators' Brochure, participant

informed consent, participant recruitment materials (if applicable), and other documentation as required by the IRB to their IRB for review and approval.

The study site will adhere to all requirements stipulated by their respective IRB. This includes notification to the IRB regarding: protocol amendments, updates to the participant informed consent, recruitment materials intended for viewing by participants, serious and unexpected AEs, reports and updates regarding the ongoing review of the trial at intervals specified by the respective IRB, and submission of final summaries to IRB.

The Investigator will promptly inform his/her IRB of all unexpected SAEs considered possibly related to the treatment or other critical safety information reported by the clinical site.

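### Section 8.3.1 holds two conflicting causality standards; applied as written, a merely suspected alternative cause makes an adverse event Not Related

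*Combined protocol and SAP*

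**What the plan says.** Section 8.3.1 tells the investigator to assess causality by two definitions.

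- The first category is headed "Related (possibly related, related"). It needs a time course that "is consistent with a causal relationship and no other cause (e.g., medical history, concomitant drugs, therapies, and complications) can be identified".
- Not Related, whose label also takes in events judged unlikely related, applies when the time course "rules out a causal relationship and/or another cause (e.g., medical history, concomitant drugs, therapies, and complications) is suspected".

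There is no category in between. The paragraph after the definitions adds: "The definition implies a reasonable possibility of a causal relationship between the event and the study drug". A list of factors to consider follows. Under one of them, the participant's other drugs "should be examined to determine whether any of them might be recognized to cause the event in question".

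The classification is used in three places:

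- **Analysis.** Section 10.5 states: "Summaries will also be provided by severity and relationship to treatment". The Synopsis plans the same.
- **IRB.** Section 12.2 requires prompt notice of "all unexpected SAEs considered possibly related to the treatment".
- **Sponsor.** Section 8.3.3 requires immediate reporting of a new SAE arising within one month after the study period if it is judged possibly related.

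On background treatment, Section 5.2 allows "Current treatment with no more than 3 prescribed psychotropic medications". Anti-epileptics used for seizures are allowed in addition.

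**The concern.** A binary causality scale normally turns on whether study drug may have contributed. Here the operative definitions turn on whether anything else may have contributed. Possibly related, the grade one would expect to hold uncertain cases, sits inside Related and carries the same exclusion.

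This population gives the rule room to act. Section 3.1 describes seizures, sleep disorders, anxiety and irritability as part of Fragile X syndrome, and Section 10.5 collects significant behavioural changes as adverse events. Medical history can therefore offer a competing explanation. Section 3.1 also names SSRIs among usual medication, and exclusion criterion 4 in Section 5.3 does not list them as a class. Section 3.3.2 itself discusses 5-HTP given together with SSRIs. An event suspected to arise from study drug acting with a concomitant drug is one a safety review would want to see as related. Under the definitions it has another suspected cause and drops out.

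Safety and tolerability is one of the three objectives in Section 3.4.1. A by-relationship table built on this rule would make the treatments look better tolerated than a reasonable-possibility standard would. The conflict also means that two events with the same facts can be coded differently, by an investigator who knows the treatment (Section 6.4).

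**Working it through.** The plan states no figure on this point, so there is none to reproduce. The check applies the two definitions and the reasonable-possibility sentence to the same events. A cause that is suspected is read as one that can be identified.

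| Event | Two definitions | Reasonable possibility |
|---|---|---|
| A. Timing fits; no other cause suspected | Related | Related |
| B. Timing fits; another cause suspected; study drug equally plausible | Not Related | Related |
| C. Timing fits; interaction of study drug with a concomitant drug suspected | Not Related | Related |
| D. Timing fits; another cause clearly more likely; nothing argues for study drug | Not Related | Not Related |
| E. Timing excludes study drug | Not Related | Not Related |

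1. Related joins its two conditions by *and*. Rows B and C meet the timing condition and fail the second.
2. Not Related joins its conditions by *and/or*. Suspicion of another cause is enough, so rows B and C meet it although timing fits.
3. Calling the event possibly related does not help, because that grade falls under the same definition as Related.
4. The concomitant-drug factor asks the investigator to look for other drugs that could cause the event. A positive answer supplies the suspicion that triggers Not Related.
5. The standards disagree only in rows B and C, and both times the definitions move the event from Related to Not Related. The bias runs in one direction.

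On size: suppose a share p of the events that meet the reasonable-possibility standard also have a suspected alternative. The Related count then falls by the fraction p. The documents give neither p nor an expected number of events, so any worked count would only return the value assumed for p.

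**The case against.** The strongest reply is that nothing is forced. The definitions are followed by the reasonable-possibility sentence, by a call for facts or arguments, and by factors that include class response pattern and pharmacology. That reads as weighing evidence. The labels in parentheses could also be taken as mapping graded judgements onto two categories, so that possibly related simply counts as Related. And if suspecting a cause differs from identifying one, row B meets both definitions at once. This stands in part: the investigator has some room. But no text says that the looser sentence overrides the definitions, and on each of these readings the section holds two incompatible answers for the same event.

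Several stronger readings are tempting, and the documents do not support them.

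- **That co-medication nearly always triggers the rule.** Taking a drug is not the same as suspecting it. Section 5.2 requires psychotropics to be stable for at least 2 weeks and anti-epileptics for 12 weeks before Screening, and both until study medication starts. Behavioural therapies must be stable throughout the study. Under Section 8.1 a pre-existing condition becomes an adverse event only if it changes after the first dose.
- **That the missing washout adds to the problem.** Carry-over from an earlier period is study drug. It is not one of the alternative causes listed in Section 8.3.1.
- **That IRB reporting as a whole is suppressed.** Section 12.2 also requires notification of serious and unexpected adverse events without a relatedness condition. Section 8.3.3 makes the site responsible for reporting SAEs to the IRB, again without one.
- **That the main safety tables are biased.** All adverse events are recorded whatever their cause (Section 8.1) and tabulated, and SAEs are summarised separately (Section 10.5).

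**Conclusion.** The concern holds as an internal inconsistency with a one-directional effect. If the definitions are applied as written, events with fitting timing and a suspected alternative cause are classed Not Related, including possible interactions between study drug and a concomitant drug. The related counts in the by-relationship summaries are then too low against the standard that the same section invokes.

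The reporting effect is limited to two triggers: prompt IRB notice of unexpected SAEs in Section 12.2, and immediate sponsor reporting of post-study SAEs in Section 8.3.3. Total adverse event and SAE counts are unaffected, as is the IRB reporting that carries no relatedness condition.

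The conclusion assumes that the investigator follows the definitions rather than the looser sentence. How often an alternative would be suspected is unknown, so the bias has a direction but no computable size. The exposed output is a descriptive split in an exploratory study of 15 participants. That limits the damage, but it is no reason to leave a contradictory rule in place.

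**What to change.** Reword the two definitions in Section 8.3.1 and repeat them in the adverse event CRF instructions:

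- **Related (including possibly related):** there is a reasonable possibility that study drug caused or contributed to the event, even if another cause is also possible.
- **Not Related (including unlikely related):** there is no reasonable possibility, because timing rules it out, or because another cause is clearly more likely and no evidence or argument points to a contribution from study drug.

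Delete the condition in Related that excludes any other cause, and the clause in Not Related that makes suspicion of another cause sufficient. Keep the listed factors as aids to judgement. The second definition should not demand that another cause explain the event completely, because Section 8.3.1 places unlikely-related events under Not Related and that threshold would displace them.

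The cost is two definitions and the matching CRF text, taken through the usual amendment approval. More events will be labelled related, including some that study drug did not cause, so the tolerability table will look slightly less favourable.
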